3. MAJOR SECONDARY ENDPOINTS

3.1. Diffusion Tensor Imaging (DTI)

Diffusion tensor imaging (DTI) quantifies the magnitude and direction of water diffusion. Areas of tissue injury have altered diffusion, thus offering a quantitative, dynamic measure of tissue integrity. The four common DTI metrics that describe water diffusion are axial diffusivity (λ_{\parallel} , diffusion along the length of a fiber tract), radial diffusivity (λ_{\perp} , diffusion across the breadth), mean diffusivity (MD, overall measure of diffusion), and fractional anisotropy (FA, degree of anisotropy of diffusion – Molyneux et

al, 2000; Fisher et al, 2000). Several animal and human studies suggest that λ_{\parallel} roughly reflects axonal integrity and λ_{\perp} roughly reflects myelin integrity (Song et al, 2002; Song et al, 2003; Song et al, 2005). DTI measures correlate with disability (Dalton et al, 2004; Amato et al, 2007). A longitudinal study of MS patients showed an increase in FA within acute MS lesions during recovery, with a concomitant decrease in λ_{\perp} suggestive of possible remyelination (Fox et al, 2011). Furthermore, the magnitude of λ_{\perp} as baseline predicted the evolution of lesions into T1 black holes (areas with more significant tissue injury) at 1 year (Fox et al, 2011). DTI is performed differently by different MRI manufacturers, which can yield different DTI values. However, with careful attention to pulse sequence implementation, we have demonstrated the ability to standardize image acquisition to yield DTI images with very similar values (Fox et al, 2012; Magnotta et al, 2012).

The DTI images will be processed at the Cleveland Clinic Mellen Center Research MRI Laboratory (Director: [name]). The images will be reviewed for quality and completeness as they are received by the lab. Images will be checked for adherence to protocol, image quality, and completeness of the electronic transfer. This step determines if the MRI dataset can be approved for DTI analysis or if it should be rejected, reacquired, or resent from NeuroRx. Once approved, the images will be analyzed. The image analysis pipeline results in numerical results recorded in a comma separated value (csv) text file. Cumulative results will be transmitted to the NeuroNEXT DCC in accordance with the procedures outlined in the corresponding data transfer agreement.

Based on this information, there will be two DTI outcomes under consideration, both measured separately on the left and right side:

- Axial Diffusivity (LD)
- Radial Diffusivity (TD)

3.2. Magnetization Transfer Ratio (MTR)

Magnetization transfer (MT) imaging is an indirect study of semi-solid tissue components such as cell membranes, whose T2 relaxation times are too short to be imaged directly (Hohol et al, 1997; Benedict et al, 2004). The MT effect is usually quantified by calculating voxel-by-voxel maps of the percent decrease in signal between images with and without MT pulse, thus producing a MTR image (Fillippi & Grossman, 2002). Decreased MTR correlates strongly with loss of myelin and axons within lesions are more pronounced in NAWM in SPMS (Feinstein et al, 2004; Marrie et al, 2005), and correlate with disability (Tedeschi et al, 2007). MTR is also abnormal in normal-appearing grey matter (NAGM) in MS (Ge et al, 2002; Fisniku et al, 2009; Fillippi et al, 2011), and recent MR/pathology correlation studies show that MTR can detect cortical demyelination (Chen et al, 2013). These findings suggest that whole-brain normal-appearing brain tissue (NABT) and gray matter MTR may be useful biomarkers of tissue damage in trials of neuroprotective therapies in MS.

A number of small, single-center studies of MS therapies have incorporated MTR. But, relatively few multi-center studies have done so, presumably because of the added complexity of standardizing acquisition protocols and performing a robust centralized analysis. Two randomized, placebo-controlled multi-center studies in SPMS (interferon beta-1b and IVIG) demonstrated annual changes in whole-brain measures of MTR of about 2.5%-3.5% in their respective placebo groups (Inglese et al, 2003; Fillippi et al, 2004). While neither study showed a benefit of treatment on MTR, the magnitude of change over time suggests that detecting a treatment effect on MTR for a neuroprotective agent in SPMS is feasible. The recent DEFINE BG-12 phase III trial in RRMS (analyzed by NeuroRX) included MTR imaging in 64 sites, with n=126-135 per treatment group. Using a similar sample size to our proposed study, a significant benefit on both whole-brain and

NABT MTR was seen in patients treated with BG-12 relative to placebo (Arnold et al, 2014). These results, combined with the ability to implement MTR imaging on most modern scanners with whole-brain coverage, high resolution, and high signal-to-noise ratio (SNR), suggest that MTR is both feasible and useful to deploy in a multi-center trial in progressive MS (Dastidar et al, 1999; Kalkers et al, 2001; De Stefano et al, 2010).

The MTR data will be transmitted to the NeuroNEXT DCC directly from NeuroRX in accordance with the procedures outlined in the corresponding data transfer agreement.

Based on this information, there will be two MTR outcomes under consideration:

- Median MTR in normal appearing brain tissue (NABT)
- Median MTR in normal appearing grey matter (NAGM)

3.3. Optical Coherence Tomography

Optical Coherence Tomography (OCT) non-invasively uses near-infrared light to measure the thickness of the retinal nerve fiber layer (RNFL) and macular ganglion cell layer (GCL), which comprise first-order sensory neurons for the visual pathway. Both RNFL and GCL decline proportional to disease progression in MS (even in the absence of overt visual systems, signs, or symptoms – Rudick et al, 1999) and brain atrophy (Gordon-Lipkin et al, 2007). OCT metrics correlate strongly with visual function (Walter et al, 2012) and patient-reported quality of life in MS (Mowry et al, 2009). Being able to selectively quantify the contributions of unmyelinated axonal (peripherally RNFL) vs. neuronal (macular GCL) pathology has substantial relevance for understanding the pathological processes in MS (Waxman & Black, 2007). Analogous to MRI, data from different OCT platforms are not equivalent; however, the change in RNFL thickness from the two main study OCT platforms (Zeiss Cirrus and Heidelberg Spectralis) can be combined in a clinical trial (Waxman et al, 2011). In summary, OCT may represent a simple, quick, non-invasive, and relatively inexpensive method to assess neurodegeneration and the potential benefit of putative neuroprotective therapies.

The OCT data will be transmitted to the NeuroNEXT DCC from the Digital Angiography Reading Center (DARC) lab in accordance with the procedures outlined in the corresponding data transfer agreement. For each subject, there is one record per eye.

For the purposes of this trial, the analysis will focus on a comparison of the mean retinal nerve fiber layer (RNFL) thickness. All subjects are assessed by either a Spectralis or Cirrus machine. For each machine, three separate measurements are obtained – unless the first two readings differ by more than 7.5%, in which case an additional reading is taken. The mean RNFL thickness (within each eye) is defined as the mean of the two variables that are closest to one another.

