6. ANALYSIS POPULATIONS

Due to the exploratory nature of this study, all analyses to address the primary and major secondary objectives will be conducted at the 0.10 significance level. The analysis population of interest will differ depending on the objectives of any particular analysis.

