The three levels of nesting represented by Equation (4) (month nested within eye nested within patient) presents a challenge for deriving power equations, and analytic results are usually based on simplifying assumptions (e.g., fewer random effects than in Equation (4)) (Heo and Leon, 2009). In order to base the power estimate on the LMM of Equation (4), a simulation approach was used. For the simulation, the LMM of Equation (4) was fit to the pilot data and then the resulting estimates were treated as parameters in the following replications. For each replication, a random number generator was used to compute random effects and random error for $N = 250$ hypothetical treatment and control patients based on the appropriate covariance structures (e.g., \mathbf{G}). Then simulated OCT response values were computed based on the fixed and random effects and random error of Equation (4). For each replication, the null hypothesis of $H_0: \delta = 0$ was evaluated with the Z-test based on a LMM fit to the simulated data. The process was repeated 1000 times for each effect size value of δ and the average number of rejections of H_0 was taken to be the estimated power. Results of the simulation are shown in the table below.

Table 9.2. Power as a Function of Effect Size based on the OCT Simulation Study

Effect Size	Power
30%	0.515
35%	0.603
40%	0.665
45%	0.782
50%	0.855

As the table shows, the power surpassed the conventional cutoff of 0.80 only for the largest effect size, but the next lower size (45%) was close to the cutoff. The results indicate that $N = 250$ might provide adequate power for the treatment and placebo slope comparison of OCT if the effect size is large, but power might be lower than the conventional cutoff for medium and smaller effect sizes.

9.6. Major Secondary Objective (d): *Evaluate the activity of Ibudilast (MN-166) versus placebo as measured by cortical atrophy, as measured by cortical longitudinal atrophy detection algorithm.*

No pilot data or other effect size estimates were available for CLADA. However, we expect CLADA effects to be consistent with those of the other secondary endpoints. Therefore, we are confident that statistical power for CLADA will be sufficient to detect effect sizes similar to those discussed for the other secondary endpoints.

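### Averaging the two closest RNFL readings gives up precision that the median of the same readings would keep, with no gain in robustness, and the number of readings is not clearly defined

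*Combined protocol and SAP*

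**What the plan says.** SAP 3.3 defines the endpoint for each eye: "The mean RNFL thickness (within each eye) is defined as the mean of the two variables that are closest to one another". On the number of readings it says that for each machine "three separate measurements are obtained – unless the first two readings differ by more than 7.5" per cent, "in which case an additional reading is taken". Taken literally, this is three readings and a fourth on disagreement. The trigger, which looks only at the first two readings, fits better with two readings and a third on disagreement. The protocol's OCT section (8.8.2.10) gives no reading sequence that would settle it.

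SAP 8.3 analyses RNFL thickness with the linear mixed model of section 7.1, comparing slopes between arms, with a further random effect for the two eyes. SAP 6 adds that "all analyses to address the primary and major secondary objectives will be conducted at the 0.10 significance level". SAP 9.5 and Table 9.2 give simulated OCT power of 0.515, 0.603, 0.665, 0.782 and 0.855 for effects of 30, 35, 40, 45 and 50%, and comment that "the power surpassed the conventional cutoff of 0.80 only for the largest effect size".

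No reason is given for the closest-pair rule. The documents state no within-visit reading SD and no rate of bad readings, and do not say whether the OCT pilot data were combined in the same way.

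**The concern.** A closest-pair rule looks like protection against a bad reading. With ordinary random error, though, two readings often agree by chance on the same side of the true value, and the rule then discards the reading that would have balanced them. That noise enters the residual variance of the RNFL slope. Among the major secondary endpoints with a stated power, OCT has the lowest figures, so precision lost from readings already in hand is worth recovering. Separately, an endpoint whose number of component readings is unclear could be computed differently by two analysts from the same data.

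**Working it through.** **1. The plan's own figure.** SAP 9.5 says the null hypothesis "was evaluated with the Z-test based on a LMM fit to the simulated data", but the pilot slope and variance components are not given, so Table 9.2 cannot be reproduced from inputs. As a consistency check, I fitted power = Φ(c × effect − 1.645), two-sided α = 0.10, with one constant. c = 5.39 gives 0.489, 0.596, 0.695, 0.783 and 0.853. Three of the five are within 2 points; the others are off by 2.6 and 3.0 points, about 2 Monte Carlo standard errors or less with 1000 replications. The table is usable as a starting point.

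**2. Three readings, independent normal error, variance in units of single-reading variance.** The closest pair drops the reading furthest from the mean of the three. Its average is the mean of three minus half that reading's deviation D, and the mean is independent of the deviations:

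- Closest pair: 1/3 + E[D²]/4 = 1/2 + √3/(4π) = 0.638
- Median: 1 − √3/π = 0.449
- Mean of any two: 0.500
- Mean of all three: 0.333

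Closest pair against median: 0.638/0.449 = 1.42 in variance, √1.42 = 1.19 in SD. Simulation agreed with the closed forms.

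**3. Outliers (simulated, three readings).** The contamination rates and sizes are assumptions.

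| Error model | Closest pair | Median | Mean of two | Mean of three | Closest pair / median |
|---|---|---|---|---|---|
| Normal | 0.638 | 0.449 | 0.500 | 0.333 | 1.42 |
| 1% of readings at 10×SD | 0.649 | 0.470 | 0.990 | 0.659 | 1.38 |
| 2% at 5×SD | 0.661 | 0.478 | 0.741 | 0.494 | 1.38 |
| 10% at 5×SD | 0.882 | 0.681 | 1.70 | 1.13 | 1.30 |
| 10% at 10×SD | 1.40 | 1.09 | 5.45 | 3.64 | 1.28 |
| t with 3 df | 0.971 | 0.720 | 1.51 | 0.997 | 1.35 |

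The median has the lower variance in every row.

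**4. A fourth reading.** With four normal readings the closest pair has variance 0.624 against 0.298 for the median, a ratio of 2.1.

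**5. Two readings, a third only on disagreement.** With normal error the probability of a third reading is 2[1 − Φ(7.5%/(√2 × CV))]. The CV is assumed. When no third reading is taken, both rules return the mean of two. Over all eyes (simulated):

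| Reading CV | Third reading taken | Closest pair | Median (mean if two) | Excess variance |
|---|---|---|---|---|
| 1% | about 0% | 0.500 | 0.500 | none |
| 2% | 0.8% | 0.511 | 0.503 | 2% |
| 3% | 7.7% | 0.556 | 0.515 | 8% |
| 5% | 29% | 0.613 | 0.513 | 19% |

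**6. Power, three readings always taken.** Let f be the share of slope-estimate variance due to reading noise. The documents do not give it, so a range is assumed. Switching to the median multiplies slope variance by 1 − f(1 − 0.449/0.638) = 1 − 0.296f. At the 40% effect, Φ⁻¹(0.665) + 1.645 = 0.426 + 1.645 = 2.071, so

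power = Φ(2.071/√(1 − 0.296f) − 1.645).

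- f = 10%: 0.676, a gain of 1.1 points
- f = 25%: 0.694, a gain of 2.9 points
- f = 50%: 0.725, a gain of 6.0 points

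**The case against.** The best defence is robustness: an occasional bad scan is the obvious reason for such a rule, and against a plain average it works. A reader might infer from the normal-error figures (0.638 against 0.500) that the rule is worse than averaging any two readings. That is not general. With 1% of readings at 10×SD, or 2% at 5×SD, the mean of two is the noisier (0.990 against 0.649, 0.741 against 0.661). This defence stands against the mean of two, but not against the median, which protects against the same bad readings with less variance.

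Second, the 42% depends on three readings always being taken. If the intended sequence is two with a third on disagreement, most eyes give the same value under either rule. This stands; the sentence does not settle which sequence applies.

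Third, reading noise is only part of the slope variance, alongside patient and eye effects that no combination rule touches. If the pilot data were processed with the same rule, Table 9.2 already includes the loss. This also stands, and limits what can be said about power.

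Finally, a reader might infer that the SAP itself calls this endpoint underpowered. It does not. It says "The results indicate that $N = 250$ might provide adequate power" if the effect is large, allows that power might fall below 0.80 for medium and smaller effects, and reports 0.855 at 50%.

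**Conclusion.** The point holds as one of efficiency and clarity. With three readings and independent normal error, the closest-pair mean has 42% higher variance than the median. That is a variance ratio and should not be read as 42% more SD, which is 19%. In the outlier models tried, the excess variance was 28% to 42%, so robustness does not justify the rule. Under the two-plus-one sequence the excess over all eyes is nil to 8% of reading variance for CVs of 1 to 3%, and larger only if readings are considerably noisier.

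A reader might infer a known loss of trial power. The documents do not support one: they give neither a reading SD nor reading noise's share of slope variance. About 1 point at a 10% share and about 3 points at 25%, for the 40% effect, are conditional on those assumed shares and on three readings. Neither bias nor invalid inference follows from the rule. The median was never worse in any scenario examined, so the change is worth making even though its benefit may be small.

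**What to change.** Before unblinding, amend SAP 3.3 to define RNFL thickness per eye and visit as the median of all acceptable readings collected, or their mean if only two exist. Keep the closest-pair value as a sensitivity analysis. Rewrite the sentence on readings to state the sequence actually used, including whether a disagreement of more than 7.5% leads to a third or a fourth reading. Say in SAP 9.5 whether the pilot OCT data used the closest-pair rule.

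Do not resolve the ambiguity by reducing the number of readings acquired: if three are now taken, dropping to two would raise the normal-error variance from 0.449 (median of three) to 0.500. The cost is a short SAP amendment and a small change to the derivation code, provided the individual readings are held or can be obtained from the OCT reading centre. No new scans are needed.

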3.4. Cortical Longitudinal Atrophy Detection Algorithm (CLADA)

Additional atrophy measures include GM atrophy, which will be measured using two different approaches – GM fraction (GMF) and cortical thickness (CTh). Cortical thickness is measured at each time point using CLADA, a longitudinal algorithm based on deformation of a patient-specific cortical model (Nakamura et al, 2011), and will be considered as an additional major secondary endpoint for this study. The cortical model is generated from longitudinal T1-weighted MPRAGE images. The point correspondence that define the distance between the inner and outer cortical surfaces are maintained throughout, leading to greater reproducibility. Change in CTh is calculated as the slope in CTh over time, with a scan-rescan variability of 0.45%.

The CTh data will be processed at the Cleveland Clinic MS MRI Analysis Center, and will part of the

same electronic data transfer containing the BPF data. In accordance with the procedures described in the corresponding data transfer agreement, the BPF analysis and verification will be completed first. After the MRI data for all study visits for a given subject have been received, the other atrophy measurements, GMF and CTh, will be measured and verified.

4. ENROLLMENT & RANDOMIZATION

Following the screening phase, subjects who continue to meet entry criteria will be enrolled and randomly assigned in a 1:1 manner to one of two treatment groups: MN-166 100 mg/d or matching placebo. A total of approximately 250 subjects will be randomized into the study. Randomization of subjects will be stratified by immunomodulation therapy status [untreated with long-term MS disease modifying therapy (DMT) vs. those receiving either glatiramer acetate (GA) or interferon beta (IFN β -1a – Avonex, Rebif, or IFN β -1b – Betaseron, Etavia)], and disease status [primary progressive MS (PPMS) vs. secondary progressive MS (SPMS)]. The NeuroNEXT DCC will generate a randomization table for each of the strata using a permuted block design with random block sizes.

5. PRELIMINARY TABULATIONS

All subjects who provide informed consent will be accounted for in this study. Regularly generated enrollment reports will describe:

- Number of subjects consented, eligible, and randomized by site
- Ongoing study status of all randomized subjects
- Reasons for ineligibility
- Protocol deviations
- Early drug withdrawals
- Early study terminations

Subject data will also be summarized by treatment group (MN-166 vs. placebo) with respect to important demographic characteristics. Distribution of categorical variables will be tabulated by treatment group. Continuous variables will be summarized as mean, median, standard deviation, minimum, and maximum by treatment group and overall. Variables to be collected will include:

- Gender
- Race
- Ethnicity
- Age
- Participation in lumbar puncture study
- T2 lesion volume (CCs) at screening

6. ANALYSIS POPULATIONS

Due to the exploratory nature of this study, all analyses to address the primary and major secondary objectives will be conducted at the 0.10 significance level. The analysis population of interest will differ depending on the objectives of any particular analysis.

6.1. Primary and Major Secondary Efficacy Analyses

6.1.1. Modified Intent-to-Treat (mITT) Population

The primary analysis for all primary and major secondary efficacy objectives will be implemented using a modified intent-to-treat (mITT) approach, which is defined as all subjects who are:

- Randomized
- Received at least one dose of study medication
- Have at least one efficacy assessment (i.e., week 24, 48, 72, or 96 visit) during the double-blind phase of the study

All subjects meeting this criteria will be analyzed based on the treatment to which they were randomized, whether or not they remained compliant with respect to taking study medication.

6.1.2. Per Protocol (PP) Population:

To assess the sensitivity of the results, and to obtain knowledge regarding the potential effects when the protocol was strictly adhered to, we will also replicate all primary and major secondary efficacy objectives using a per protocol population. The per-protocol population includes the subset of all mITT subjects who satisfy both of the following conditions:

- Have 75% -125% compliance (both limit values inclusive) with assigned study medication as randomized in the double-blind phase
- Have no major protocol deviations (defined as any alteration/modification to the protocol that has the potential to negatively impact subject safety, integrity of the study, ability to draw conclusions from the study data, or affect the subject's willingness to participate in the study)

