All imaging endpoints will be statistically evaluated using linear mixed models (LMMs: Laird and Ware 1982). LMMs are advantageous for longitudinal clinical trials because they can account for the dependency due to repeated measures with relatively few parameters, which potentially enhances statistical efficiency. Furthermore, LMMs can accommodate incomplete cases (ie, missing data), which is expected in this study due to dropout. LMMs are typically estimated using maximum likelihood methods (Verbeke and Molenberghs 2000) that yield valid inferences with incomplete cases under the widely applicable assumption that the missing data are ignorable (Little and Rubin 2002). For all analyses, the residuals of the fitted statistical models will be examined for evidence of departure from assumptions, such as normality. If assumptions appear to be grossly violated, then transformations of response variables might be considered. Alternatively, generalized LMMs might be used because of their ability to accommodate a wider range of distributional forms (eg, beta distribution). The primary analysis will be conducted using a modified intent-to-treat analysis, which includes all subjects who are randomized and receive at least one dose of study medication in the double-blind phase. Since this is a phase 2 proof of concept study, statistical significance will be determined by any test that exceeds the 0.10 significance level. To account for baseline imbalance due to randomization vagaries, the baseline group means (intercepts) in the statistical analysis will be constrained to be equal. Sensitivity analyses will be conducted using brain atrophy as measured by SIENA and covariate adjustment for covariates with potential impact on atrophy (ie, non-steroidal anti-inflammatory drugs [NSAIDs]) that were unbalanced between treatment groups.

Safety Analysis:

The safety analyses will be conducted using the double-blind safety population, defined as subjects who are randomized and receive at least one dose of study medication in the double-blind phase.

Adverse events (AEs), discontinuation due to AEs, and serious adverse events (SAE) will be summarized by presenting, for each treatment group, the number and percentage of subjects with any AE, and AEs by system organ class and preferred term. Adverse events will be further summarized by severity and by relationship to study drug. The summary will be limited to treatment-emergent AEs.

Sample Size Justification:

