7.3.1. Follow-up Procedures Upon Discontinuation/Withdrawal

If a subject discontinues study medication for any reason, the subject will be encouraged to continue to be followed within the study, but on a reduced study visit schedule. Depending upon when the subject discontinued study drug, the reduced study visit schedule will include study visits at Week 24, 48, 72, and 96. The timing of all study visits will remain relative to the original baseline date. For subjects who discontinue study drug between regularly scheduled study visits, the subject should complete the next regularly scheduled study visit after study drug discontinuation, and then shift to the reduced study visit schedule. For subjects who discontinue study drug at a regularly scheduled study visit, the subject should shift immediately to the reduced study visit schedule. For subjects discontinuing study drug but remaining in the study for follow-up, study visits will occur on an approximate semi-annual basis until Week 96. Table 2 outlines the procedures and assessments to be conducted in subjects remaining in the study for follow-up but are off study medication. After study drug discontinuation, new-onset AEs will not be collected.

If a subject discontinues/withdraws prior to study completion and does not wish to continue follow-up within the study (i.e. return for semi-annual visits), then all assessments scheduled for the Early Withdrawal visit (Table 2) should be performed at the time of study discontinuation.

A termination CRF page should be completed for every subject who received study medication whether or not the subject completed the study. The reason for discontinuation should be indicated on the CRF. Any AEs that are present at the time of discontinuation/ withdrawal should be followed in accordance with the safety requirements outlined in Section 11.

For all subjects who complete the study on study medication, a follow-up visit (Week 100) will be conducted 4 weeks after the last visit to assess general health and adverse event status.

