Between scheduled study visits, subjects with new or significant worsening MS symptoms that last 24 hours in duration and occur in the absence of fever or infection should notify the Investigator immediately and be seen for an Unscheduled Relapse Evaluation Visit within 3 days of notifying the Investigator. The following assessment should be performed at the Relapse Evaluation Visit:

- Body weight
- Vital signs
- Interval history
- Adverse event monitoring
- Concomitant medication review
- SF-36
- MSIS-29
- SBQ-R
- BPI
- EDSS by blinded neurologist

Subjects continuing follow-up off study medication do not need to return for Unscheduled Relapse Evaluation Visits. If during a regularly scheduled study visit, a relapse episode is noted, complete the relapse evaluation assessments above along with the scheduled assessments for that study visit.

Semi-Annual Visits (for subjects who discontinue study medication)

Subjects who discontinue study medication and remain in the study for follow-up will be followed on a semi-annual basis (Week 24, 48, 72, and 96, relative to Baseline). The following assessments will be performed at each semi-annual visit:

- Relapse assessment
- Cognitive tests (SDMT and SRT)
- BPI
- SF-36
- MSIS-29
- EQ-5D
- SBQ-R
- MSFC

- EDSS
- Brain MRI
- OCT

Early Withdrawal Visit

Subjects who discontinue study medication and choose not to be followed on a semi-annual basis will undergo the following assessments:

- Physical examination
- Body weight
- Vital signs
- Interval history
- Adverse event monitoring
- Concomitant medication review
- Cognitive tests (SDMT and SRT)
- BPI
- SF-36
- MSIS-29
- EQ-5D
- SBQ-R
- Hematology, chemistry, lipid profile, and urinalysis lab
- Serum biomarker samples
- ECG (12-lead)
- MSFC
- EDSS
- Brain MRI
- OCT
- Lumbar puncture (optional)
- Return of used/unused study drug bottles, study drug accountability and compliance check

Laboratory Re-test visit

Subjects who have a clinically significant abnormal lab finding may return for a laboratory re-test visit and will have the following assessments performed at the discretion of the CSSPI:

- Interval history
- Hematology, chemistry, or urinalysis lab, as indicated

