12.1. Data Analysis

12.1.1. Analysis Populations

The modified Intent-to-Treat (mITT) Population: The primary population for analysis is the mITT, which is defined as all subjects who are randomized and receive at least one dose of study medication and have at least one efficacy assessment in the double-blind phase. Subjects will be analyzed based on the treatment they are randomized.

The Per Protocol (PP) Population: The per-protocol population includes all mITT subjects who satisfy the following conditions:

- Have 75% -125% compliance, both limit values inclusive in the double-blind phase,
- Have no major protocol deviations, determined by a blinded data review.

Commented [CCS1]: OPTIONAL – We removed this from the SAP, since this is repetitive with the second criteria in that you can't have 75%-125% compliance without taking the study medication as randomized. If others feel we don't need to change this, I'm fine with that.

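### SAP 6.1.1's list of qualifying visits excludes a subject whose only post-baseline scan is the Early Withdrawal MRI, and SAP 3.4 does not cover subjects with a missing scan: minor points, free to correct

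*Combined protocol and SAP*

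**What the plan says.** **Analysis set.** SAP 6.1.1 covers BPF and the major secondary endpoints alike: "The primary analysis for all primary and major secondary efficacy objectives will be implemented using a modified intent-to-treat (mITT) approach". Besides randomisation and one dose, its entry condition is "Have at least one efficacy assessment (i.e., week 24, 48, 72, or 96 visit) during the double-blind phase of the study". Protocol 12.1.1 and the synopsis paragraph on analysis populations ask only that subjects "have at least one efficacy assessment in the double-blind phase", with no list of visits. The closing part of SAP 7.1 also gives no list. One sentence in the synopsis under Endpoint Analysis is looser still, describing a set "which includes all subjects who are randomized and receive at least one dose of study medication in the double-blind phase".

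**Scans from early leavers.** Protocol 8.8.1.2 says: "Subjects who discontinue study medication and choose not to be followed on a semi-annual basis will undergo the following assessments". The list that follows, like Table 2, includes brain MRI and OCT. For those who stop drug, protocol 7.3.1 says "the subject will be encouraged to continue to be followed within the study, but on a reduced study visit schedule". That schedule is Weeks 24, 48, 72 and 96, with MRI at each.

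**Model.** SAP 7.1 enters time in weeks and justifies the mixed model partly by its use of incomplete cases. For the categorical-time model only, it assigns off-schedule visits to the next scheduled one.

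**Cortical thickness.** SAP 3.4 has BPF processed first. Grey-matter fraction (GMF) and cortical thickness (CTh) follow: "After the MRI data for all study visits for a given subject have been received". SAP 8.4 then uses a model like that of 7.1.

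**The concern.** The abbreviation that opens the SAP 6.1.1 parenthesis makes it a closed list. It turns away a subject who has a baseline and a post-baseline BPF value, and it does so on an event after randomisation that treatment can influence. Early discontinuation is itself a tolerability endpoint, so such exclusions could fall unevenly between the arms. Nothing in the model requires the exclusion, and the protocol does not ask for it.

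The SAP 3.4 sentence raises a related problem. For a subject who drops out or misses a scan, the stated trigger never occurs. If the laboratory took it literally, no CTh value would exist for that subject, and placing the subject in the mITT set could not supply one. The stake would be the completeness of a major secondary endpoint.

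**Working it through.** **1. The plan's own figure.** The 125 per arm cannot be reproduced, because the pilot slopes and variance components are not given. Only the dropout step can be checked. Multiplying as the SAP does, 113 × 1.10 = 124.3, which rounds up to 125. Dividing instead, 112 / 0.90 = 124.4, also 125. No power figure is given for CLADA.

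**2. Who is affected by SAP 6.1.1.**

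| Subject (randomised and dosed) | SAP 6.1.1 | Protocol 12.1.1 |
|---|---|---|
| Leaves study before Week 24, Early Withdrawal scan done | out | in |
| Leaves study before Week 24, no post-baseline assessment | out | out |
| Leaves after at least one scheduled efficacy visit | in | in |
| Stops drug, attends scheduled follow-up | in | in |

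Only the first row differs. In the third row, no text removes a later Early Withdrawal scan.

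**3. How many.** Assume dropout is uniform over 96 weeks. Leavers before Week 24 = 250 × d × 24/96:
- d = 5%: 3.1
- d = 10% (the SAP's figure): 6.25
- d = 20%: 12.5

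If half of a 10% dropout came before Week 24, the count would be 12.5. These are upper limits, since not every leaver will have the scan.

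**4. Effect on power.** Take the common-intercept model with random intercepts and slopes, scans at Weeks 0, 24, 48, 72 and 96, and 125 per arm. Assumed inputs, none of them in the documents: with 96 weeks as the unit of time, intercept SD 10, slope SD 0.5 or 1, residual SD 0.5 to 2, and the Early Withdrawal scan 12 weeks after the last scheduled one. Let R be the variance of the slope difference relative to using every scan, and set power at 80% when every scan is used. At two-sided 0.10,

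power = Φ[(1.645 + 0.842)/√R − 1.645].

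Excluding the pre-Week-24 leavers gives:
- 10% dropout: R = 1.0003 to 1.0011, power 79.96% to 79.99%
- 20% dropout: R = 1.0008 to 1.0024, power 79.92% to 79.97%

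The loss is below 0.1 percentage point throughout.

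**5. SAP 3.4, if applied as a completeness condition.** At 10% dropout, 25 of 250 subjects would have no CTh value, leaving 125 × 0.90 = 112.5 per arm, before counting anyone with a single missed scan. The same formula gives:
- 10% dropout: R = 1.037 to 1.055, power 78.1% to 78.7%
- 20% dropout: R = 1.084 to 1.123, power 75.8% to 77.1%

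A cruder rescaling, Φ[2.487 × √(112.5/n) − 1.645], gives 79.7% if the 80% belongs to n = 125/1.10 = 113.6, and 76.2% if it belongs to n = 125.

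**The case against.** **CLADA.** A reader might infer from SAP 3.4 that the CLADA analysis is restricted to completers. The documents do not support that. The sentence can be read as an order of processing: BPF first, then GMF and CTh. Waiting for a subject's scans also suits a method whose cortical model is built from longitudinal images. Nothing says that a subject with fewer than five scans goes unprocessed. SAP 6.1.1 places this endpoint in the mITT set, and SAP 8.4 uses a model that takes incomplete cases. What remains is that the trigger, taken literally, never arrives for some subjects and no fallback is given.

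**Populations.** A reader might also count three primary populations by adding the one-dose sentence in the synopsis. But the synopsis's own definition requires an efficacy assessment, as does protocol 12.1.1, and protocol 12.1.2 refers back to 12.1.1. So there is one definition, one loose sentence and one narrowing parenthesis in the SAP.

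**Off-schedule visits.** It can be said that SAP 7.1 already absorbs off-schedule scans. That rule is written for the categorical-time model and allocates visits, not subjects, so it does not widen 6.1.1.

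**Size.** The case that this is small is right. Patients who stop drug are steered into scheduled follow-up and so qualify.

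**Conclusion.** This is a minor point that holds as stated. SAP 6.1.1 is narrower than the protocol and SAP 7.1, and it leaves out usable data from a subject whose only post-baseline scan is a pre-Week-24 Early Withdrawal MRI. At most about 6 of 250 subjects are affected under uniform 10% dropout, with a negligible effect on power. SAP 3.4 has a gap that conflicts with 6.1.1 and 8.4 only if applied literally. It would then cost about 1 to 2 percentage points of power at 10% dropout under the model assumptions above, or up to about 4 on the cruder rescaling.

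A reader might infer a sizeable bias from a completers-only CTh analysis. That rests on inputs the documents do not give. Suppose dropout is 15% in one arm and 5% in the other:
- Leavers decline at twice their arm's overall mean rate: the shift in slope difference is 0.15/0.85 − 0.05/0.95 = 0.124 of the placebo slope.
- Leavers decline at twice the completers' rate: the shift is 0.15/1.15 − 0.05/1.05 = 0.083.
- Equal dropout, under either assumption: the shift is zero.

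These values compare completers with the true mean, not with a mixed model on all scans, which would itself be biased if dropout depended on unobserved slope. They are therefore not the cost of this wording and do not raise the importance of the point.

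**What to change.** - **SAP 6.1.1:** state that any post-baseline MRI (or OCT, for that endpoint), including one at the Early Withdrawal visit, counts as an efficacy assessment, and enters the model at its actual week.
- **Synopsis, Endpoint Analysis:** bring the one-dose sentence into line with the synopsis's own population definition and protocol 12.1.1.
- **SAP 3.4:** reword so that CTh and GMF are measured on all available scans once the subject's last available scan has been received. Check that the data transfer agreement it refers to says the same.

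The cost is a few sentences, plus processing of scans already acquired. No visit, procedure or sample-size change is needed.
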